The Baseline visit occurs between 14 to 31 days after the screening visit, depending on the required washout period following discontinuation of excluded therapies. Eligibility must be confirmed prior to randomization. At the Baseline visit, the following procedures and assessments are to be performed, preferably in the order shown below:

- Ask the subject to complete the DLQI, HADS, and ESS questionnaires
- Assess and record any changes in the subject's concomitant medications
- Assess and record any changes in the subject's medical history
 - Female subjects should be queried regarding history of, or current, breast masses or abnormal discharge, and history of mammography (if applicable), and history of abnormal vaginal bleeding or discharge
- Review menstrual diary and record dates of menstrual flow (if applicable)
- Assess AE's and record SAEs caused by protocol-mandated interventions
- Obtain vital signs
- Perform a urine pregnancy test for females of childbearing potential and confirm the subject has a negative urine pregnancy test result prior to randomization (with positive or equivocal results confirmed by a serum pregnancy test)
- Confirm subject's eligibility based on the inclusion/exclusion criteria (to include review of eDiary compliance for eligibility)
- Randomize subject in IWRS if eligibility confirmed
- Perform targeted physical examination, including weight
- Perform IGA PN-A

- Perform IGA PN-S
- Obtain photos (at selected sites, only subjects that signed photography consent)
- Dispense study drug; subjects will take loading dose of 3 tablets while on site
- Review eDiary for compliance, re-train subject as needed
- Assess and record any post-dose AEs and SAEs
- Confirm next scheduled visit

6.5.5 *Week 1 Telephone Contact Visit*

The Week 1 visit is a telephone visit that occurs 7 days (\pm 3 days) after the Baseline visit. At the Week 1 visit, the following procedures and assessments are to be performed:

- Assess and record any changes in the subject's concomitant medications
- Assess and record any AEs and SAEs
- Review eDiary for compliance, re-train subject as needed
- Confirm next scheduled visit

6.5.6 *Week 2 Visit*

The Week 2 visit occurs 14 days (\pm 3 days) after the Baseline visit. At the Week 2 visit, the following procedures and assessments are to be performed:

- Assess and record any changes in the subject's concomitant medications

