### 6.1.3 Visit Windowing

[figure not shown]
Data will be summarized based on nominal visit indications. Due to protocol revisions, differing follow-up visit schedules were used. Data collected during post-treatment follow-up will be summarized as

Protocol Version(s)	Nominal Visit	Analysis Visit
V2.0; V2.1	3-Week Follow-up	3-Week Follow-up
V2.0; V2.1	5-Week Follow-up	5-Week Follow-up

V3.0	Post-Drug Observation Day 3	3-Day Follow-up
V3.0	Post-Drug Observation Day 7	1-Week Follow-up
V3.0	Post-Drug Observation Day 14	2-Week Follow-up
V3.0	Post-Drug Observation Day 21	3-Week Follow-up
V3.0	Post-Drug Observation Day 28	4-Week Follow-up
V3.0	Post-Drug Observation Day 35	5-Week Follow-up

In addition, a "Latest Follow-up" visit will be summarized, which will include the latest available follow-up information for each subject from the 3-, 4-, 5- Week Follow-up visits.

Information collected at early treatment discontinuation visits will be mapped to the most appropriate visit based on the midpoints between scheduled visits.

For example, if a subject terminates use of study drug on or after Day 22 but before Day 36, data collected at the early end of treatment visit will be mapped to the Week 4 evaluation for summaries. If the subject has Week 4 values present, the data collected at the early end of treatment visit will not replace the data collected at Week 4. For the sensitivity efficacy analyses, last observation carried forward (LOCF) will be applied subsequent to mapping the information to the appropriate visit.

Additionally, WI-NRS will be summarized at Weeks 1, 2, 3, 4, 5, 6, 7, 8, 9, 10 and 3- and 5-Week Follow-up by averaging the daily results for the 7 days prior to each week. The weekly average values will be calculated if a subject has at least four responses during the 7 day range, as defined below:

Week/Visit	Study Day Range
Week 1	2-7 (as Day 1 may be pre or post first dose)
Week 2	8-14
Week 3	15-21
Week 4	22-28
Week 5	29-35
Week 6	36-42

Week 7	43-49
Week 8	50-56
Week 9	57-63
Week 10	64-70
3-Week Follow-up	Post-treatment days 15-21
5-Week Follow-up	Post-treatment days 29-35

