### 6.9.3 Clinical Laboratory Evaluation

Clinical safety laboratory values will be measured by a central laboratory. Summary statistics for actual values and for changes from baseline will be tabulated for laboratory results by scheduled visit.

Subjects with clinical laboratory values outside of the normal reference range at any post-baseline assessment will be summarized. Shifts from baseline laboratory values will be tabulated, with the exception of most reproductive endocrinology laboratory values.

Serum follicle-stimulating hormone, luteinizing hormone, estradiol, progesterone and antimullerian hormone will be summarized separately for women using hormonal contraception/therapies and those not using hormonal contraception/therapies.

By-subject listings of all laboratory data, as well as abnormal laboratory results, will be presented.

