	Likely Unrelated	xx ( xx.x%)	xx ( xx.x%)

<sup>a Counts reflect numbers of subjects reporting one or more TEAEs that map to the MedDRA. At each level of summarization (System Organ Class or Preferred Term) subjects are counted once under the greatest reported relationship.

Note: TEAEs are AEs with an onset after first dose of study drug.

MedDRA Version 21.1.

Table 14.3.1.4.1.1: Summary of Hematology Laboratory Results (Safety Population)
(Page 1 of xx)

	Placebo	Serlopitant 5 mg
	(N=xxx)	(N=xxx)
<test name=""> (<units>)</units></test>		
Baseline		
n	XX	XX
Mean	XX.X	XX.X
SD	XX.XX	XX.XX
Median	XX.X	XX.X
Min. to Max.	xx to xx	xx to xx
Week 2		
n	XX	XX
Mean	XX.X	XX.X
SD	XX.XX	XX.XX
Median	XX.X	XX.X
Min. to Max.	xx to xx	xx to xx
Absolute Change from Baseline		
n	XX	XX
Mean	XX.X	XX.X
SD	XX.XX	XX.XX
Median	XX.X	XX.X
Min. to Max.	xx to xx	xx to xx

Note: No imputation of missing values. Baseline is the latest recorded value prior to first dose of study drug. Change calculated as post-baseline – baseline. "Latest Follow-up" visit includes the latest available follow-up information for each subject from the 3-Week or 5-Week Follow-up visits.

SOURCE: USERNAME\SPONSOR\PROJECT\JOBNAME (DATE,TIME)

Table to include post-baseline visits of "Week 2", "Week 10", "3-Week Follow-up", "5-Week Follow-up", "Latest Follow-up".

Table to include following lab tests: "BASOPHILS", "EOSINOPHILS", "HCT", "HGB", "LYMPHOCYTES", "MCH", "MCHC", "MCV", "MONOCYTES", "NEUTROPHILS", "PLATELET COUNT", "RBC", "WBC".

Table 14.3.1.4.1.2: Shift Summary of Hematology Laboratory Results (Safety Population)
(Page 1 of xx)

<test name=""> (<units>)</units></test>		Placebo (N=xxx)			Serlopitant 5 mg (N=xxx)	
		Week 2			Week 2	
Baseline	BNL	WNL	ANL	BNL	WNL	ANL
BNL	xx (xx.x%)	xx ( xx.x%)	xx ( xx.x%)	xx ( xx.x%)	xx ( xx.x%)	xx ( xx.x%)
WNL	xx ( xx.x%)	xx ( xx.x%)	xx ( xx.x%)	xx ( xx.x%)	xx ( xx.x%)	xx ( xx.x%)
ANL	xx ( xx.x%)	xx ( xx.x%)	xx ( xx.x%)	xx ( xx.x%)	xx ( xx.x%)	xx ( xx.x%)
		Week 10			Week 10	
Baseline	BNL	WNL	ANL	BNL	WNL	ANL
BNL	xx ( xx.x%)	xx ( xx.x%)	xx ( xx.x%)	xx ( xx.x%)	xx ( xx.x%)	xx ( xx.x%)
WNL	xx ( xx.x%)	xx ( xx.x%)	xx ( xx.x%)	xx ( xx.x%)	xx ( xx.x%)	xx ( xx.x%)
ANL	xx ( xx.x%)	xx ( xx.x%)	xx ( xx.x%)	xx ( xx.x%)	xx ( xx.x%)	xx ( xx.x%)
	3-	-Week Follow-up		3-	Week Follow-up	
Baseline	BNL	WNL	ANL	BNL	WNL	ANL
BNL	xx ( xx.x%)	xx ( xx.x%)	xx ( xx.x%)	xx ( xx.x%)	xx ( xx.x%)	xx ( xx.x%)

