Absolute Change from On-Drug Baseline		
n	XX	XX
Mean	XX.X	XX.X
SD	XX.XX	XX.XX
Median	XX.X	XX.X
Min. to Max.	xx to xx	xx to xx

Note: On-Drug Baseline is the latest recorded value prior to last dose of study drug. Change calculated as post-baseline – baseline. SOURCE: USERNAME\SPONSOR\PROJECT\JOBNAME (DATE,TIME)

Table to include parameters in following order: "Temperature (degrees Celsius)", "Respiration Rate (breaths/min)", "Heart Rate (beats/min)", "Systolic Blood Pressure (mmHg)", "Diastolic Blood Pressure (mmHg)".

Table to include post-drug observation visits of "3-Day Follow-up", "1-Week Follow-up", "2-Week Follow-up", "3-Week Follow-up", "4-Week Follow-up", "5-Week Follow-up".

Table 14.3.1.7.1: Summary of Hospital Anxiety and Depression Scale (HADS)

(Safety Population)

(Page 1 of xx)

	Placebo	Serlopitant 5 mg
	(N=xxx)	(N=xxx)
<subscale></subscale>		
Baseline		
n	XX	XX
Mean	XX.X	XX.X
SD	XX.XX	XX.XX
Median	XX.X	XX.X
Min. to Max.	xx to xx	xx to xx
Week 4		
n	XX	XX
Mean	XX.X	XX.X
SD	XX.XX	XX.XX
Median	XX.X	XX.X
Min. to Max.	xx to xx	xx to xx
Absolute Change from Baseline		
n	XX	XX
Mean	XX.X	XX.X
SD	XX.XX	XX.XX
Median	XX.X	XX.X
Min. to Max.	xx to xx	xx to xx

Note: Baseline is the latest recorded value prior to first dose of study drug. Change calculated as post-baseline – baseline. "Latest Follow-up" visit includes the latest available follow-up information for each subject from the 3-Week, 4-Week or 5-Week Follow-up visits.

SOURCE: USERNAME\SPONSOR\PROJECT\JOBNAME (DATE,TIME)

Table to include subscales in following order: "Anxiety Subscale", "Depression Subscale".

Table to include post-baseline visits of "Week 4", "Week 10", "3-Week Follow-up", "5-Week Follow-up", "Latest Follow-up".

Table 14.3.1.7.2: On-Drug Summary of Hospital Anxiety and Depression Scale (HADS) (Safety Population Consenting to Protocol Version 3.0) (Page 1 of xx)

	Placebo	Serlopitant 5 mg
	(N=xxx)	(N=xxx)
<subscale></subscale>		
Baseline		
n	XX	XX
Mean	XX.X	XX.X
SD	XX.XX	XX.XX
Median	XX.X	XX.X
Min. to Max.	xx to xx	xx to xx
Week 4		
n	XX	XX
Mean	XX.X	XX.X
SD	XX.XX	XX.XX
Median	XX.X	XX.X
Min. to Max.	xx to xx	xx to xx
Absolute Change from Baseline		
n	XX	XX
Mean	XX.X	XX.X
SD	XX.XX	XX.XX
Median	XX.X	XX.X
Min. to Max.	xx to xx	xx to xx

Note: Baseline is the latest recorded value prior to first dose of study drug. Change calculated as post-baseline – baseline. SOURCE: USERNAME\SPONSOR\PROJECT\JOBNAME (DATE,TIME)

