#### Listing sorted by Subject.

 Day is calculated as date - date of first dose for dates prior to first dose. Otherwise, day is calculated as
 date - date of first dose + 1 for dates on or after first dose.
Note: ITT = Intent-to-Treat Population; S = Safety Population; PP = Per-Protocol Population.
SOURCE: USERNAME\SPONSOR\PROJECT\JOBNAME (DATE, TIME)

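### The visit mapping sends many early-discontinuation lab, HADS and ESS values, and some ECG values, to visits that have no row in the by-visit safety tables

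*SAP*

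**What the plan says.** SAP 6.1.3 gives the rule for subjects who stop drug early: "Information collected at early treatment discontinuation visits will be mapped to the most appropriate visit based on the midpoints between scheduled visits". Its only example says that "if a subject terminates use of study drug on or after Day 22 but before Day 36", the data go to Week 4. If Week 4 is already filled, "the data collected at the early end of treatment visit will not replace the data collected at Week 4".

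Protocol Appendix A, Table 2, schedules labs, ECG, HADS and ESS at the early-discontinuation visit. The SAP shells fix which on-treatment visits each by-visit table displays:

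- Hematology (Table 14.3.1.4.1.1): "Table to include post-baseline visits of 'Week 2', 'Week 10', '3-Week Follow-up', '5-Week Follow-up', 'Latest Follow-up". Chemistry (Table 14.3.1.4.2.1) has the same list, and both shift tables follow it.
- Endocrine labs (Table 14.3.1.4.3.1.1): Week 10 only.
- HADS (Table 14.3.1.7.1): "Table to include post-baseline visits of 'Week 4', 'Week 10', '3-Week Follow-up', '5-Week Follow-up', 'Latest Follow-up". ESS (Table 14.3.1.8.1) has the same list.
- ECG parameters and ECG shifts (Tables 14.3.1.5.1.2 and 14.3.1.5.1.3): Weeks 2, 4 and 10.
- Vital signs (Table 14.3.1.6.1): Weeks 2, 4, 6 and 10.

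No shell has an end-of-treatment row, and the Latest Follow-up row draws only on follow-up visits at 3, 4 or 5 weeks. For labs, SAP 6.9.3 adds: "Subjects with clinical laboratory values outside of the normal reference range at any post-baseline assessment will be summarized". The table index has no shell for that summary; it has only a listing of out-of-range results (Listing 16.2.8.2.2).

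**The concern.** The rule assigns a visit without regard to the assessment, while the tables show different visits for different assessments. In the SAP's own example the data go to Week 4, but the hematology and chemistry tables have no Week 4 row. Values collected by design at the moment a subject stops drug can therefore drop out of the means and shift tables.

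Safety, tolerability and physical dependence are stated objectives. Protocol 5.6 names persistently abnormal thyroid tests and abnormal prolactin, cortisol or corticotropin among possible grounds for stopping, so a value taken at stopping may itself be the signal. As an illustration, take a subject who stops on Day 40 with a new abnormal chemistry value. The value is mapped to Week 6, so the chemistry mean and shift tables show the Week 2 and follow-up values but nothing from the time of stopping.

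**Working it through.** **Inputs**
- First dose is Day 1: the SAP listings compute study day as "date - date of first dose + 1 for dates on or after first dose".
- Target days (Protocol 6.5): "The Week 2 visit occurs 14 days" after Baseline, which is Day 15. Weeks 4, 6 and 10 fall 28, 42 and 70 days after Baseline, which are Days 29, 43 and 71.
- Possible early stop days: Day 2 to Day 70, which is 69 days.

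**Step 1: reproduce the SAP example.** Midpoints of adjacent visits are (15 + 29)/2 = 22 and (29 + 43)/2 = 36, exactly the SAP's Week 4 limits. The others are (1 + 15)/2 = 8 and (43 + 71)/2 = 57. Assessment-specific calendars do not reproduce the example. An ECG calendar (Weeks 2, 4, 10) would end the Week 4 window at (29 + 71)/2 = 50. A HADS/ESS calendar (Weeks 4, 10) would run it from (1 + 29)/2 = 15 to 50. A lab calendar (Weeks 2, 10) has no Week 4. The rule therefore uses the general calendar, including Week 6.

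**Step 2: count stop days per window.** Nearest Baseline, Days 2–7: 6. Week 2, Days 8–21: 14. Week 4, Days 22–35: 14. Week 6, Days 36–56: 21. Week 10, Days 57–70: 14. Total: 6 + 14 + 14 + 21 + 14 = 69.

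**Step 3: compare with the table rows.** The last column assumes that scheduled visits are attended on their target day.

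| Measure | On-treatment rows | Stop days mapped to a visit with no row | Share of 69 | Further stop days lost to non-replacement |
|---|---|---|---|---|
| Hematology, chemistry | Weeks 2, 10 | 22–56: 14 + 21 = 35 | 51% | 15–21: 7 (10%) |
| HADS, ESS | Weeks 4, 10 | 8–21 and 36–56: 14 + 21 = 35 | 51% | 29–35: 7 (10%) |
| ECG parameters, shifts | Weeks 2, 4, 10 | 36–56: 21 | 30% | 15–21 and 29–35: 14 (20%) |
| Endocrine, if drawn | Week 10 | 8–56: 14 + 14 + 21 = 49 | 71% | none |
| Vital signs | Weeks 2, 4, 6, 10 | none | 0% | 15–21, 29–35 and 43–56: 28 (41%) |

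The endocrine line is conditional because footnote 5 to Protocol Table 2 ties those tests to Screening, Week 10 and Follow-up. The six days nearest Baseline are not counted in any column.

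**Step 4: vary the assumptions.** Shares of days equal shares of subjects only if stopping is spread evenly. With assumed front- or back-loaded stopping (exponential, 3-week scale), the no-row share is 33–51% for hematology and chemistry, 39–51% for HADS and ESS, and 13–34% for ECG. If the Week 1 telephone contact counts as a scheduled visit, it takes Days 5–11. Under even spread the counts become 42 (61%), 38 (55%) and 28 (41%).

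**Step 5: test remapping by assessment.** With assessment-specific midpoints every mapped post-baseline visit has a row, but non-replacement still drops values. Labs mapped to Week 2 (Days 8–42) lose Days 15–42, 28 of 69. ECG loses Days 15–21 and 29–49, 7 + 21 = 28 of 69. HADS/ESS mapped to Week 4 (Days 15–49) lose Days 29–49, 21 of 69.

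**The case against.** Several points on the other side stand.

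- ECG is the weakest case. Table 14.3.1.5.1.1 counts treatment-emergent PR, QRS and QTc abnormalities without visit rows, so a discontinuation ECG can still be counted there. The loss is confined to by-visit parameters and shifts.
- For labs, SAP 6.9.3 commits to a summary that does not depend on visit mapping, although no shell carries it out. Protocol 7.1.3 has clinically significant abnormal findings after first dose recorded as adverse events, and those that lead to stopping appear in Table 14.3.1.1.3. All values are listed.
- For HADS and ESS, subjects who consented to protocol Version 3.0 have post-drug values from Day 3 onward in Tables 14.3.1.7.3 and 14.3.1.8.3. With a half-life of 45–86 hours (Protocol 1.5.1), some drug is still present then. This is partial cover: it is limited to those subjects and does not show the discontinuation-visit value. Nor does the on-drug baseline there (SAP 6.9.4.7) take in a value recorded after the final dose.
- The reference to the most appropriate visit leaves some discretion, but the only example points to the general calendar.
- The tables are descriptive; no hypothesis test depends on them.

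A reader might also infer a subject count. In the Phase 2 PN study, 9 of 128 subjects stopped for TEAEs; 9/128 × 280 = 19.7, and half of that is about 10. The documents do not support this as an estimate. It pools arms that split 3 serlopitant to 6 placebo; with about 64 per arm, serlopitant alone gives 3/64 × 140 = 6.6, and half is about 3. It also assumes even stop timing and omits stops for other reasons.

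**Conclusion.** The gap is real and modest. Followed as written, SAP 6.1.3 leaves discontinuation-visit values without a row on about half of possible stop days for hematology, chemistry, HADS and ESS, and on about three in ten for by-visit ECG displays. Non-replacement adds to this. These shares rest on the general calendar, which the SAP example confirms, and on counting days rather than subjects.

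Two stronger readings are tempting, but the documents do not support them. One is that the values vanish from every summary; the routes described above rule that out. The other is that the tables will flatter serlopitant. The direction of any between-arm bias is unknown, and in the Phase 2 PN study more placebo than serlopitant subjects stopped for TEAEs. The primary endpoint is untouched, because WI-NRS comes from the daily eDiary with its own day ranges.

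**What to change.** - Add a row for the last on-treatment value, stated to include the early-discontinuation visit, to the lab, HADS, ESS and by-visit ECG summary tables and to the lab and ECG shift tables. Define the row in SAP 6.1.3 and state that the non-replacement rule does not apply to it.
- Add a table shell for the out-of-range lab summary that SAP 6.9.3 already promises.
- Do not rely on remapping by assessment alone. It still drops the values shown in Step 5, and it would place a lab value from a Day 43 stop in the Week 10 row, four weeks from its true time.

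The cost is SAP wording, one row per table and one shell. No new data, visits or procedures are needed, and the change can be made before unblinding. The downsides are slightly longer tables and a row that mixes exposure durations.

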### 6.1.4 Adjustments for Covariates

Analysis of covariance will include baseline value as a covariate.

### 6.1.5 Handling of Dropouts or Missing Data

Should a determination of treatment period (on treatment, pre-treatment, post-treatment) be required for AEs or concomitant medication but the corresponding date is missing, or is a partial date, the event/medication will be considered on treatment unless the portions of the date that are available indicate this is not possible.

The primary method of handling missing efficacy data will be Markov Chain Monte Carlo (MCMC) multiple imputation. Imputation will be conducted within each treatment group independently, so the pattern of missing observations in one treatment group cannot influence missing value estimations in another. For each imputation process, 25 imputations will be performed.

Subjects that withdrew from the study due to lack of efficacy will have missing values imputed, however, the WI-NRS responder status will be defined as non-responder. Subjects that used an excluded therapy to treat worsening of pruritus or PN will have data values collected after the use of the excluded therapy set to missing and subsequently imputed. These subjects will also have the WI-NRS responder status defined as non-responder.

Missing WI-NRS data will be derived for the analysis using the method of MCMC multiple imputation. The 4-point responder status will be derived from imputed WI-NRS values. Since both primary and key secondary endpoints require WI-NRS, the following steps will be followed:

- 1. Using the daily eDiary data, calculate Baseline and Week 1 through Week 10 values by averaging available values. In order to compute a week's average, a minimum of 4 values must be available for that week. The weekly average will be imputed when there are fewer than 4 values available.
- 2. From step 1, create a dataset for each treatment group, of subjects with observed values and those needing estimation by MCMC. The missing WI-NRS values in each dataset

will be filled in using the MCMC method to generate 25 datasets. The resulting datasets for each treatment group will be combined into one complete dataset.

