5.6 Study Drug Discontinuation

Subjects should be discontinued from study drug treatment in the following situations:

- A female subject desires to become pregnant at the current time, stops contraception or expels her intrauterine device/implant, or becomes pregnant
- A female subject has new breast findings (e.g. a palpable mass or abnormal mammography, discharge), or has abnormal vaginal discharge or bleeding
- The subject decides to discontinue study drug treatment, or withdraws consent from the study
- The subject receives a strong CYP3A4 inhibitor (See [Appendix B](#))
- Any medical condition that may jeopardize the subject's safety if study drug is continued, in the investigator's and/or Sponsor's opinion; this may include the development of persistently (2 successive occasions) abnormal thyroid function tests (TSH >10, or TSH > 6 with low free T4; TSH <0.1, or TSH < 0.35 with high free T4); abnormal morning prolactin, cortisol, or corticotropin levels; or signs and symptoms of adrenal insufficiency

- Discontinuation is deemed to be in the best interest of the subject, in the investigator's and/or Sponsor's opinion, including evidence that the subject does not meet inclusion/exclusion criteria intended primarily for safety reasons, or a persistent lack of adherence to study procedures

The Sponsor or designee should be contacted within 24 hours of investigator's awareness of any study drug treatment discontinuation. Investigators should make every effort to contact the Sponsor or designee before discontinuing study drug treatment, if possible.

Subjects who discontinue treatment with study drug prior to completing the treatment period will enter a 5-week follow-up (post-study drug observation) period following the last dose of study drug (see [Section 3.1](#), [Section 6.5.10](#)). Every effort should be made for subjects to complete the 5-week observation period and the Follow-up visit after a subject has discontinued from study drug.

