normal; eradication of *Helicobacter pylori* infection generally requires a negative urea breath test and fecal antigen test and endoscopy; and the viral load should be undetectable if viral infections such as hepatitis B or hepatitis C, or HIV were previously diagnosed. Any previously active skin disease is considered to be well controlled if it is globally considered clear or almost clear (permissible to have post-inflammatory pigmentation, fine scale, faint pink erythema, barely perceptible induration/papulation, and no oozing or crusting).

Use of gentle cleansers and bland emollients (including those with urea) is encouraged for all subjects. If bland emollient use is elected, it must be initiated at least 2 weeks (14 days) prior to Baseline visit, and continued throughout the treatment period.

Treatment with non-systemic corticosteroids or antihistamines that do not involve skin application (e.g. inhaled, intranasal, ophthalmic, or intra-articular) is allowed.

Leukotriene inhibitors will be permitted for treatment of conditions other than PN (e.g. asthma).

5.7.2 *Excluded Therapies*

Initiation or use of topical therapy with corticosteroids, calcineurin inhibitors, calcipotriene, PDE-4 inhibitors is not permitted within 4 weeks prior to the Baseline visit or throughout the treatment period, but such therapy may be initiated during the follow-up period if needed.

Initiation of bland emollient is not permitted within 2 weeks (14 days) prior to Baseline visit or throughout the treatment period, but such therapy may be initiated during the follow-up period if needed.

The following therapies and activities are excluded from the Screening visit through the treatment period, and through the follow-up period:

- NK₁-R antagonists (other than study drug)
- Systemic immunosuppressive/ immunomodulatory therapies (including but not limited to systemic corticosteroids, PDE-4 inhibitors, cyclosporine, mycophenolate-mofetil, methotrexate, azathioprine, thalidomide, interferon-gamma, or phototherapy)
- Biologic therapies (other than therapies such as insulins, vaccines)
- Strong CYP3A4 inhibitors (See [Appendix B](#))
- Use of an indoor tanning facility, or natural sun exposure resulting in significant tanning or sunburn
- Any investigational therapy

The following therapies and activities are excluded from the Screening visit through the treatment period, and use is discouraged, though permitted, through the follow-up period:

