⁷See Table 3 for eDiary assessments

⁸During the period between informed consent and first study drug dose, only SAEs caused by a protocol-mandated intervention will be collected.

Table 3 Schedule of eDiary Assessments

An eDiary device is provided to subjects at the Screening visit and collected at the Follow-up visit.

Device	Assessment	Frequency and Duration of Assessment
eDiary	WI-NRS	Once daily from Screening/Mid-Screening visit through the Follow-up visit
eDiary	Dosing	Once daily from Baseline visit through Week 10 visit or study drug discontinuation

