### 6.7 Analysis of Efficacy

The efficacy endpoints will be summarized within the ITT and PP populations using descriptive statistics by time point and treatment. Available results including averaged imputed values, as well as change from baseline, will be summarized for each applicable time point. The WI-NRS and change from baseline will also be presented for each study day in a by-subject listing.

For the 4- and 3-point responder rate endpoints, subjects will be considered responders if they have at least a 4- / 3-point reduction between baseline and the corresponding week. Subjects that discontinued study drug due to lack of efficacy or used an excluded medication to treat worsening of pruritus or PN will be considered non-responders.

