#### 7. DETERMINATION OF SAMPLE SIZE

This study will use a 5% two-sided alpha level. While the alpha level is two-sided, clinically relevant results require a serlopitant benefit.

The target sample size of 280 randomized and dosed subjects (140 per group) has been determined based upon a 1:1 allocation of subjects to treatment groups and a 5% alpha level. Completed Phase 2 studies indicate that placebo responder rates vary between 20% and 25% and serlopitant rates between 33% and 47%. A sample size of 280 subjects provides >90% power assuming a placebo responder rate of CCI and serlopitant rate of CCI.

The sample size calculations have been performed in PASS 13 ("PASS 13 Power Analysis and Sample Size Software" 2014) and use a Chi-Squared test. The primary analysis will control for the stratification factors. It is expected that this unstratified power estimate will under-estimate the true power as it does not take the variance reduction resulting from stratification into account (Matts 1988).

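### The rescue non-responder rule depends on the word 'excluded', which changes meaning by study period, so some early stoppers could count as Week 10 responders while on anti-itch therapy

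*SAP*

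**What the plan says.** **Rescue rule.** SAP 6.1.5: "Subjects that used an excluded therapy to treat worsening of pruritus or PN will have data values collected after the use" of the therapy set to missing and then imputed, with responder status fixed as non-responder. SAP 6.7 repeats that those who "used an excluded medication to treat worsening of pruritus or PN will be considered non-responders". Protocol 8.2 and 8.9.1 and SAP 6.8.1 use the same trigger. None gives a study day or study period for it.

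**What is excluded, and when.** Protocol 5.7.2 bars topical corticosteroids, calcineurin inhibitors, calcipotriene and PDE-4 inhibitors during treatment, "but such therapy may be initiated during the follow-up period if needed". For topical anti-pruritics and systemic anti-pruritics (H1 antihistamines, doxepin, gabapentin, pregabalin and others), "use is discouraged, though permitted, through the follow-up period".

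**Early stoppers.** Under Protocol 5.6, subjects who stop drug "prior to completing the treatment period will enter a 5-week follow-up (post-study drug observation) period", counted from the last dose.

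**Diary and window.** Protocol Appendix A, Table 3 schedules the WI-NRS "Once daily from Screening/Mid-Screening visit through the Follow-up visit". For early stoppers that visit is 35 (+3) days after the last dose (Protocol 6.5.11). SAP 6.1.3 fixes Week 10 at Days 64-70 and requires at least four entries. Neither document limits the primary analysis to on-drug scores.

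**The concern.** The trigger is a status that changes when a subject moves from the treatment period to follow-up, whereas the endpoint window is fixed by study day. Take two subjects who start gabapentin on Day 50 for worsening itch. The one still on study drug is a non-responder. The one who stopped drug on Day 40 for an adverse event is, on the period-based reading, using something permitted. The rule does not apply, and the score recorded on gabapentin decides the primary endpoint.

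Early stopping happens after randomisation and can differ by arm, so any resulting bias can differ by arm. The planned supporting analyses would not show it:

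- The Week 10 value is observed, so LOCF leaves it alone and reuses the same trigger.
- The repeated-measures model uses observed data.
- The tipping-point analysis varies only subjects with missing data.
- The Per Protocol set keeps subjects who stop for a related adverse event.

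For earlier stoppers, whose Week 10 value is imputed, weekly means recorded on a permitted therapy still feed the imputation model.

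**Working it through.** **1. The plan's own figure.** SAP 7: "This study will use a 5% two-sided alpha level"; "The target sample size of 280 randomized and dosed subjects (140 per group"), chi-squared test, power above 90%. The design rates are redacted, so this cannot be reproduced exactly. With n = 140 and p̄ the mean of the two rates,

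power = Φ{ [(p2 − p1) − 1.96·√(2p̄(1 − p̄)/n)] / √([p1(1 − p1) + p2(1 − p2)]/n) }.

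At the ends of the quoted Phase 2 ranges: 20% vs 33% gives 69.5%; 20% vs 47%, 99.8%; 25% vs 33%, 31.3%; 25% vs 47%, 97.3%. As a working pair I use 20% vs 38%: (0.18 − 1.96 × 0.0542)/0.0532 = 1.386, so power is 91.7%.

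**2. Who can have an observed Week 10 value.** With last dose on Day L, the diary runs to Day L+35 (up to L+38). Entries in Days 64-70:

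| L | to L+35 | to L+38 |
|---|---|---|
| 28 | 0 | 3 |
| 29 | 1 | 4 |
| 32 | 4 | 7 |
| 35 | 7 | 7 |

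Four entries need L ≥ 32, or L ≥ 29 with the full visit window.

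**3. How many.** In the Phase 2 PN study (Protocol 1.5.3), 3 serlopitant and 6 placebo subjects stopped for TEAEs; 128 were randomised 1:1. Assuming 64 per arm:

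- serlopitant: 3/64 × 140 = 6.6
- placebo: 6/64 × 140 = 13.1

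Days 32-69 are 38 of the 69 possible early-stop days. If stops are evenly spread, 6.6 × 38/69 = 3.6 and 13.1 × 38/69 = 7.2 fall in the window. From Day 29 (41/69) the figures are 3.9 and 7.8. These are upper counts for TEAE stops, before asking who starts a permitted therapy.

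**4. What that could do.** Let f be the share of an arm that stops in the window, starts a permitted therapy and is not caught by the rule, and r the share of those with a 4-point drop. Each arm's rate rises by f × r. All f and r are assumptions. Steps 3's 7.2/140 and 3.6/140 are about 5% and 2.5%, so the second row below assumes every such stopper starts therapy.

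| f placebo / serlopitant | power from 91.7%, r = 0.25 | r = 0.5 | r = 1 |
|---|---|---|---|
| 5% / 5% | 91.1% | 90.4% | 89.3% |
| 5% / 2.5% | 89.2% | 86.2% | 79.2% |
| 2.5% / 5% | 93.0% | 94.1% | 95.9% |

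If both arms truly respond at 25% and f is 2.5% placebo and 5% serlopitant, the chance of a significant result favouring serlopitant rises from 2.5% to 4.2% (r = 0.5) or 6.7% (r = 1).

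**5. Sensitivity to a few subjects.** One subject is 1/140 = 0.7 percentage points. Unstratified chi-square without correction: 35 vs 52 responders gives p = 0.028; 36 vs 52, p = 0.039; 37 vs 52, p = 0.054. This starting point was chosen near the boundary.

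**The case against.** **The rule may fire after all.** It has no period limit, the therapies sit under the heading for excluded therapies, and the SAP's Per Protocol criterion speaks of plausible effect on the Week 10 endpoint. A programmer could apply it to any use before Day 70. This stands: a reader might infer that the rule certainly fails for early stoppers, and the documents do not settle that. The period reading is still the more natural one. Protocol 5.7.2 records use of an excluded therapy as a deviation, which permitted use would not be, and Protocol 5.7.3, which points to 8.2, concerns rescue during treatment.

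**The diary may be gone.** Appendix A, Table 2 marks eDiary collection at Early Treatment Discontinuation. If the device is returned then, a subject stopping before the window has no observed Week 10 score and is imputed. Table 3 and Protocol 6.1.1 and 6.5.11 point the other way. The conflict is real and unresolved.

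**Not all early stoppers are affected.** SAP 6.7 makes those who stop drug for lack of efficacy non-responders whatever they take. Systemic immunosuppressants, biologics and other NK1 antagonists stay excluded through follow-up. Both limits stand. The first is itself inconsistent: SAP 6.1.5 and Protocol 8.2 require withdrawal from the study, not from drug.

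**The effect is small, and may run against the drug.** On the Phase 2 split, a net two extra placebo responders needs uptake times response of 2/(7.2 − 3.6) = 56% in both arms, and Protocol 1.3 says first-line topicals often work inadequately. This stands as to size.

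**It is an estimand choice.** Counting permitted off-drug therapy as part of outcome fits an intent-to-treat philosophy. But the plan already treats rescue as failure for subjects on drug, and it states no different intent for those off it.

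**Conclusion.** The gap holds in a limited form. The same therapy, started on the same day for the same reason, can make one subject a non-responder and leave another an observed responder, depending on whether drug had been stopped. Two programmers could derive different primary endpoints from the same data.

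It applies to stops from about Day 29-32, for reasons other than lack of efficacy, followed by a therapy that 5.7.2 allows in follow-up. It also requires that the subject keeps the diary and that exclusion is read by period.

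The likely pool of TEAE stoppers is about 4 serlopitant and 7 placebo per 140, given 64 per arm in Phase 2 and even stop days. Stops for other reasons are not counted, because the documents give no rate. A reader might scale all Phase 2 TEAE stops to 7 and 13 per 140, but that ignores the diary cutoff. A reader might also infer a bias towards serlopitant. The documents support no fixed direction, and the Phase 2 split would point towards lost power.

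**What to change.** Change the analysis definition only, before unblinding, in SAP 6.1.5, 6.7 and 6.8.1 and Protocol 8.2 and 8.9.1. For the responder endpoints, state that set-to-missing and non-responder status apply when all of the following hold, whether or not the subject is still on study drug:

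- the therapy is one that Protocol 5.7.2 excludes during the treatment period, leaving out bland emollients;
- it is used to treat worsening of pruritus or PN, as the rule now requires;
- it is used on or before the last day of the analysis window: Day 70 for Week 10, Day 28 for Week 4, Day 14 for Week 2.

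Reconcile two pairs of passages: Appendix A Tables 2 and 3 on whether the eDiary is collected at early treatment discontinuation, and SAP 6.7 with SAP 6.1.5 and Protocol 8.2 on whether lack of efficacy means stopping drug or leaving the study. The care rules in 5.7.2 stay as they are.

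The cost is wording. Protocol 5.7 already records treatment period and indication for concomitant therapies through follow-up, so no new data are needed. The downside is that a few early stoppers who improved on permitted therapy become non-responders.
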